 - b. Relationships between clinical and laboratory values will be evaluated in longitudinal mixed effect models. We will develop models that capture the combined frequency and severity of disease manifestations while accounting for age of onset, protoporphyria subtype (EPP and XLP), and genotype. A sample size of 150 (assuming a minimum of 3 follows ups per patient, a correlation of 0.7 among outcomes over time from the same subject, a variance of outcome equal to 1 and a compound symmetric covariance structure) yields 91% power to detect a moderate interaction ($\beta=0.4$) between time and an associated factor of interest.
 - c. A severity score based on predictive demographic and clinical characteristics will be developed
 - d. After 100 participants are enrolled, the mean score of the Hospital Anxiety and Depression Scale (HADS) will be computed and compared to the general population value. A sample size of 100 yields 90% power to detect a 20% difference in HAD-scale between the general population and our sample at the .05 significance level. The illness Perception Questionnaire and EPP/XLP-specific questionnaire will also be scored.
 - e. During this interim look at $n=100$, we will re-evaluate the estimates used in our initial power calculation that yielded a sample size of 150 and determine whether the study needs to be extended beyond this point to examine correlations of QoL scale scores with clinical severity and genotypes

Sponsors (federal, state, foundation and industry support): National institutes of Health (NIH)

1. Protocol Overview

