The objective of this protocol is to conduct a systematic multidisciplinary investigation of the erythropoietic protoporphyrias, including the natural history, morbidity, psychosocial issues, and genotype-phenotype correlations in people with EPP and XLP. The research questions are:

- A. To characterize the natural history and clinical variability (e.g., age of onset, severity, progression) in EPP and XLP participants.
- B. To establish genotype-phenotype correlations and identify markers of disease severity.
- C. To understand the impact on quality of life and psychosocial issues experienced by pediatric and adult EPP/XLP patients
- D. To chronicle the use, and potential benefits and risks of current and emerging therapies for the erythropoietic porphyrias.

3. Background

Porphyrias are metabolic diseases that result from deficiencies of specific enzymes of the heme biosynthetic pathway (Figure 1). Heme is the prosthetic group for a variety of essential hemoproteins, including respiratory cytochromes, catalase, nitric oxide synthase, myoglobin, etc. Heme synthesis occurs in all tissues but is most active in bone marrow and liver. The bone marrow requires large amounts of heme for hemoglobin and the liver utilizes heme in large amounts for cytochrome P450 enzymes (CYPs). The DNA sequences and chromosomal locations are established for the human genes of the enzymes in this pathway, and multiple disease-related mutations have been found for each.

[figure not shown]

Figure 1. Enzymes and intermediates in the heme biosynthetic pathway and diseases associated with deficiencies of each enzyme. Mitochondrial and cytosolic enzymes are noted in red and tan backgrounds, respectively. Porphobilinogen deaminase (PBG-deaminase or PBGD) is also known as hydroxymethylbilane synthase (HMB-synthase or HMBS)[1].

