- 1) Participants and their family members known to the investigators who can be re-contacted and consented for inclusion, or who have previously consented for the procedures that are part of this study.
- 2) Individuals referred by the American Porphyria Foundation with known or suspected porphyria.

- 3) Individuals referred by physicians and other sources.

4.A. Inclusion criteria

There will be no exclusions based on age, race, ethnicity, or gender for this study. Inclusion criteria are based on 1) clinical features, 2) biochemical findings, as documented by laboratory reports of porphyria-specific testing performed after 1980, and 3) molecular findings documenting the identification of a mutation in a porphyria-related gene. Absolute values are preferred for diagnostic biochemical thresholds. Fold increases in comparison to an upper (or lower) limit of normal (ULN or LLN) are also acceptable, but are complicated by considerable variation between laboratories in normal limits. Equivocal biochemical measurements may require confirmation by a consortium reference laboratory. Provision is made for enrolling relatives who may not have symptoms but have biochemical or molecular documentation of a porphyria.

1. Enrollment in the Longitudinal Study of the Porphyrins (7201)
2. Willing to sign informed consent form (and provide assent if participant is a minor)
3. Biochemical findings- A marked increase in erythrocyte protoporphyrin [total erythrocyte protoporphyrin >200 ug/dL, or more than 1.5-fold increase (relative to ULN of 80 ug/dL)], with a predominance of free protoporphyrin (85-100% in EPP and 50-85% in XLP).
4. Molecular findings – one of the following:
 - a. A disease causing FECH mutation trans to the IVS3-48C>T low expression FECH allele
 - b. Two disease-causing *FECH* mutations
 - c. A gain-of-function *ALAS-2* C-terminal deletion/exon 11 mutation (in XLP)

If no mutation is found and subjects fulfill criteria 1-3 they are eligible for enrollment

We expect to enroll 150 patients with EPP/XLP.

4.B. Exclusion Criteria

We will exclude cases with elevations of porphyrins in urine, plasma or erythrocytes due to other diseases (i.e. secondary porphyrinuria or porphyrinemia), such as liver and bone marrow diseases [Gibson 2000]. We will also exclude patients with a prior diagnosis of porphyria that cannot be documented by review of existing medical records or repeat biochemical or DNA testing.

4.C. Recruitment and Enrollment of Subjects

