Each participating site will perform a systematic review of its medical record system dating from January 1, 1980, if feasible, to the present in order to identify eligible participants currently living who were diagnosed with porphyria but are not yet enrolled this study. Records of other sources described in section 4.C. will be reviewed, when available and as appropriate. Those persons identified through medical record review who are living and who can be contacted will be offered enrollment in the prospective component of this study. .

The National Death Index (NDI) will be used to supplement identification on mortality of any patient whose vital status cannot be ascertained with certainty based on study follow-up. This will be accomplished by preparing a computerized list for submission to NDI containing the requisite information needed by them to search their files, including the date last known to be alive. This will provide the means to determine survivorship status on any enrolled patient whose status is uncertain owing to follow-up limitations, and primarily those participants whose follow-up was limited by information available from medical record review.

4.E.3. Data Items

Case Report Forms (CRFs) will be completed during Study Visits or by telephone or email interview by the Study Coordinator and/or Investigator to obtain the following data. As per 4.E.1, study visits for this study may be coordinated with LS study visits. This means also that, once a subject is enrolled in this study, data collected and entered into the DMCC data capture system for the LS will be linked to this study Information to be collected for this study which is captured in the CRFs described in detail above includes:.

Baseline:

- Eligibility
- Enrollment/demographic information
- Clinical data to include:
 - Prenatal and neonatal history (for pediatric participants)
 - Medical history
 - For females, pregnancy and menstrual history
 - Lag time for diagnosis (from onset of symptoms to time of diagnosis)
 - Diagnostic laboratory values at presentation- erythrocyte protoporphyrin values (including free and zinc fractionation), and plasma total porphyrins
 - Prior EPP treatments, (names, dosage and efficacy)
 - Concomitant medications
 - Porphyria-related complications
 - Other conditions and their complications

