1. Identification of a representative, nonbiased sample of participants with EPP and XLP. Our goal is to build cohorts of participants that will be representative of each type of erythropoietic protoporphyria. In any study of this type, the initial enrollment will likely favor longer term cases and under-represent those with very severe disease. We will monitor for disease-severity bias but believe that this bias will not be problematic or in any case will lessen with time. If necessary, we may stratify data analysis by features such as severity and age of onset, and thereby derive estimates of effects even within under-represented segments of the population. Under these circumstances and for some conditions, these stratified estimates of effects will be more valuable than the overall estimates.

We will also characterize enrollees at baseline, in terms of severity of the genotype, biochemical findings and clinical features, and record disease sequelae that have occurred from onset of symptoms to enrollment. Even if we cannot enroll persons at the time of diagnosis, we can try to properly characterize their status at time of enrollment, including both the severity of the underlying defect as well as the consequences or sequelae of the condition that have exerted effects from onset to enrollment. Thus, data collection at enrollment will include information about severity of the genetic and clinical features such as age of onset and at diagnosis. We will ascertain number and severity of disease sequelae and frequency of medical care and requirement for treatment. Thus, a number of such variables will be included as either main effects or as covariates in our analysis to account for disease status at enrollment so that we can focus on changes that have occurred during follow-up.

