6. Statistical Considerations

6.A Analysis Plan

General Statistical Considerations

Natural history study and genotype analyses: This is an observational study aimed to provide a systematic description of the severity and clinical course of each patient with the EPP phenotype, develop a severity score and correlate genotype with phenotype for EPP and XLP. Continuous variables representing patient demographic and clinical characteristics will be summarized using means and standard deviations or medians and quartiles as appropriate, while categorical variables will be summarized by frequencies with 95% confidence intervals.

A major objective will be to identify the FECH and ALAS2 mutations in each patient with the EPP-phenotype. In patients with the phenotype and no detectable FECH or ALAS2 mutations identified, a second independent blood sample will be obtained to confirm the absence of FECH and ALAS2 mutations, followed by whole exome sequencing. Exome analysis will be performed at the Mount Sinai Institute for Genomics and Multiscale Biology as described above in more detail.

Clinical and Laboratory Analyses: Clinical and laboratory measurements will be collected/described at each visit. We will develop models that capture the combined frequency and severity of disease manifestations while accounting for age of onset, protoporphyria subtype (EPP and XLP), protoporphyrin levels and genotype. To account for multiple observations obtained for each patient during the follow-up, we will develop linear mixed effects models that account for the main effect of interest and its change over time, correlated data associated with repeat measurements on the same persons, random effects of clinical center and patient, as well as the effects of confounding variables and any modifiers of the main effect. To assess the statistical significance of the effects of biochemical levels alone and these levels by age of patient, we will use a t-test to evaluate whether the coefficient of the interaction between biochemical level alone and biochemical levels by age differs from zero.

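### The severity models must account for age of onset, but enrollable symptom-free participants have no onset age, and section 6.A gives no rule for keeping them in the models or treating their onset as censored

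*Combined protocol and SAP*

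**What the plan says.** - **Models.** Section 6.A, Clinical and Laboratory Analyses, requires models of the combined frequency and severity of manifestations "while accounting for age of onset, protoporphyria subtype (EPP and XLP), protoporphyrin levels and genotype". The synopsis (Statistical Considerations, item 2b) repeats the requirement: "accounting for age of onset, protoporphyria subtype (EPP and XLP), and genotype".
- **Description.** Research question A in section 2 is "To characterize the natural history and clinical variability (e.g., age of onset, severity, progression) in EPP and XLP participants". The general rule in 6.A is "Continuous variables representing patient demographic and clinical characteristics will be summarized using means and standard deviations or medians and quartiles as appropriate". No time-to-event or censored summary is planned.
- **Meaning of onset.** The baseline items in section 4.E.3 include "Lag time for diagnosis (from onset of symptoms to time of diagnosis", so onset is onset of symptoms. Section 4.G uses the term in the same way.
- **Who may enter.** Section 4.A: "Provision is made for enrolling relatives who may not have symptoms but have biochemical or molecular documentation of a porphyria". It excludes nobody on age. Neither the numbered inclusion criteria nor the case definition in section 4 requires symptoms.
- **Collection.** Section 4.I, challenge 1, says "data collection at enrollment will include information about severity of the genetic and clinical features such as age of onset and at diagnosis" and that variables of this kind will enter the analysis as main effects or covariates. It gives no code for a participant with no onset so far.

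**The concern.** Take three possible participants: a proband with onset at 3, a symptom-free relative aged 30, and an infant sibling identified at age 1 before any symptoms. Only the first has an age of onset. The other two have an observed severity near zero, which is information the models should use, but a regression cannot use a record whose covariate is blank.

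The value is not missing by accident. It is absent because the outcome, symptom frequency and severity, is at its floor. Losing these records therefore selects on the outcome, and any genotype that tends to leave carriers symptom-free loses most people. The onset-adjusted part of the genotype-phenotype work would understate differences between genotypes. The description of onset under question A would lean young, because those still waiting for onset are left out.

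**Working it through.** **1. Does the text supply a rule?** The models need age of onset (6.A, synopsis). Onset means first symptom (4.E.3, 4.G). Symptom-free relatives and infants may enter (4.A). No section gives a coding for no onset, a missing-covariate rule, a censored analysis, or an analysis set for these people. The optional stratification in 4.I uses age of onset again, so it does not place them.

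**2. The plan's own figure that depends on the number analysed.** Table 6-1 gives power 0.91 for N = 150, ρ = 0.7, β = 0.4. It can be reproduced with a repeated-measures interaction F test, two equal groups and m = 3 measurements, if the groups differ by β at the last visit only (the plan does not state the mean pattern):
- f² = (0.4/2)² × 2/9 = 0.00889, so f = 0.0943
- λ = f² × N × m/(1 − ρ) = 0.00889 × 150 × 3/0.3 = 13.3, with 2 and 296 df
- Power = 0.912, against 0.91 stated.

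With assumed losses, power is 0.906 (2%, N = 147), 0.896 (5%, N = 142), 0.879 (10%, N = 135) and 0.836 (20%, N = 120). At small shares the loss of precision is minor. The issue is bias.

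**3. Bias in a cross-sectional genotype difference.** Assumptions: severity = N(0,1) + 0.5 × genotype, two equal genotype groups, and the symptom-free are the lowest fraction on an index correlated r with severity. Share of the 0.5 SD difference retained after they drop out (simulation):

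| Correlation r | 3% | 5% | 10% | 20% |
|---|---|---|---|---|
| 0.8 | 0.92 | 0.88 | 0.82 | 0.74 |

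That is shrinkage of about 8%, 12%, 18% and 26%. At r = 1.0 the retained share runs from 0.87 (3%) to 0.59 (20%). At r = 0.5 it runs from 0.97 to 0.90. The direction never changes.

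A simpler check takes the symptom-free to be exactly the lowest tail f of a normal scale. The mean of those kept rises by φ(q)/(1 − f), where q is the f-quantile. This gives 0.05, 0.11, 0.20 and 0.35 SD for f = 2%, 5%, 10% and 20%.

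**4. Onset summary.** Assumptions: lognormal onset, median 3 years, log-SD 1, age at assessment uniform on 1 to 60, everyone eventually symptomatic.
- True median 3.0; true upper quartile 3 × exp(0.674) = 5.9.
- Summary of those with onset so far: 2.8 and 5.3 (about 7% are censored).
- Kaplan-Meier: 3.0 and 5.9.

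A second set (true median 4 years, enrolment age uniform on 2 to 70) gives observed-only medians of 3.8, 3.5 and 3.1 at log-SD 0.8, 1.2 and 1.6, with 5%, 9% and 14% symptom-free.

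**5. Check on the remedy.** In the data of step 3 (r = 0.8), a model that keeps everyone but adds a symptomatic indicator gives a genotype coefficient of 0.91, 0.87, 0.79 and 0.70 of the full difference at 3%, 5%, 10% and 20%. The participants are kept, but the coefficient is now a contrast within symptom status. The model without onset returns the full difference by construction.

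**The case against.** The best opposing case is about scope and size, and much of it stands.

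- **Deletion is not written.** A reader might infer that the plan orders these patients to be dropped. It does not. Accounting for onset could be done with categories or an indicator, and section 4.I allows strata as well as covariates. Dropping out is only the default when no rule is given. The absence of a rule is what stands.
- **Question B as a whole does not lose its low end.** The synopsis plans correlations of quality-of-life scores, clinical severity measures and genotype, and 6.A plans a summed severity score and genotype correlations. None has an onset term. The HADS primary outcome is also untouched.
- **The main model interest is change over time.** Section 6.B puts it in the time-by-covariate interaction. If slopes are independent of baseline severity, the same selection leaves that interaction essentially unattenuated (ratio about 1.00).
- **The group may be small.** Section 3 places onset in early childhood, and numbered criterion 3 requires a marked protoporphyrin rise. The provision for relatives in 4.A is worded more loosely than that list, and the two should be reconciled.
- **A larger onset bias is tempting but mistaken.** If 10% never develop symptoms (about 16% symptom-free at assessment), Kaplan-Meier gives 3.4 and 7.9 years against 2.8 and 5.3. Most of that gap comes from counting the never-symptomatic in the denominator: 3 × exp(Φ⁻¹(0.75/0.9)) = 7.9. That is a different quantity and should not be reported as bias in age of onset.
- **Diagnostic lag.** A reader might expect negative lags to be averaged for people diagnosed before symptoms. No section plans this.

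**Conclusion.** The point holds for the onset-adjusted severity models and for the description of age of onset. The plan requires a covariate that some eligible participants cannot have, and it does not say what happens to them. By default they leave the models, on the basis of the outcome, and onset is summarised only among those who have reached it.

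The direction is clear; the size is not known. The 8% to 26% shrinkage rests on an assumed symptom-free share of 3% to 20%, a 0.8 correlation, a 0.5 SD difference and a cross-sectional contrast. The shift in onset of about 0.2 years in the median and 0.6 years in the upper quartile rests on the assumed lognormal and age distributions. If nearly every enrollee has symptoms, both effects are small. The documents do not support a claim that the whole genotype-phenotype aim, the primary outcome or the power statement fails. It is worth correcting because the change is confined to the analysis.

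**What to change.** In section 6.A, with the synopsis brought into line:

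1. **Onset.** Describe age of onset by Kaplan-Meier or cumulative incidence, by subtype and genotype, with symptom-free participants censored at age at last assessment. Report the number symptom-free and, separately, the summary among those with onset, so that the two quantities are not confused.
2. **Severity models with all participants.** State one of two forms. Either use a symptomatic-to-date indicator with onset nested in it (or onset categories including one for no onset to date), or fit the model without onset and use onset only in a stated symptomatic-only analysis. The first keeps everyone and the term the plan requires, but its genotype coefficient is conditional on symptom status (step 5 of the working). Where the overall genotype difference is the target, the model without onset is the one to read.

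Cost: wording, one extra survival analysis and one extra model term, or a second model. Symptom status and age at last assessment should already be obtainable from the visit data. The Kaplan-Meier estimate needs a caveat: recruitment through diagnosed patients, referrals and the patient foundation over-represents symptomatic people, and censoring does not correct that.

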As with the Longitudinal Study of the Porphyrias, baseline visits can take place either (1) at a Participating Clinical Center (PCC), (2) arranged locally with the patient's own physician, with data and samples sent to the PCC, as needed, or (3) by telephone or email interview by the site coordinator, with data collected during the interview and arrangements made for sample collection, as needed. For visits where the participant cannot come to a PCC, all medical records must be forwarded to the site coordinator (including lab tests and physician notes). The questionnaires can be completed via phone, email or fax by the participant and sent to the site coordinator. For these visits the site coordinator is permitted to email the questionnaires to the participant and these can be returned by mail, email or fax. Once returned the coordinator should review them and if any issue need clarification contact the participant. The medical history and family history should be done via phone interview for the baseline visit.

If the study visits or sample collections takes place in facilities supported by the local institutions Clinical and Translational Science Award (CTSA), the protocol will be reviewed by any additional Advisory Committee, as appropriate, prior to implementation at the site. Centers in the Porphyrias Consortium may assist each other in data collection and data entry. The subject will be informed of the consortium arrangement and that their protected health information (PHI) will be shared with one or more other Porphyrias Consortium institutions, when approved by the IRB at each site. See Table 1 for the specific CRFs to be completed at Baseline.

Follow-up Assessments: New data as described below will be collected every 1-2 years, or more frequently if the subject experiences any significantly worsening porphyria-specific symptoms (liver disease, worsening sun sensitivity, etc) or has new study-related information to share with the study team. These overall scheduling plans may be modified based on clinical circumstances or if there is reason to anticipate a change in clinical course. Data collected during these follow-up visits will be entered onto the CRFs, see Table 1 for the specific CRFs to be completed for follow ups.

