- 1) Characterizing EPP and XLP Illness Perception via the Illness Perception Questionnaire, dermatology-specific QOL via the Dermatology Life Quality Index and EPP-specific QOL via the EPP/XLP specific questionnaire. The mean and standard deviation of each scale in our sample will be assessed.
- 2) Scores for all four QOL assessments will be analyzed; FECH and ALAS 2 mutations correlations will be sought with clinical parameters, disease severity score and genotypes.

Secondary analyses will inform whether a study extending beyond 100 patients will be needed to examine correlations of QOL scale scores with clinical severity and genotypes.

6. B Power Calculation

For the proposed analyses, the statistical powers are of two sided tests, with 0.05 level of significance.

Linear mixed effects model: We may assume, for example, that 150 participants will have at least 3 follow up visits per subject. Taking into account the correlation among outcomes over time from the same subject, the main interest is in determining whether the regression coefficient of the interaction between time and covariate of interest is zero or not. Using GPower 3.0, Table 6-1 shows the results when the variance of outcome is equal to 1, where ρ and β denote correlation among repeated outcome measures and effect size of the interaction, respectively. In this calculation, we assume compound symmetry for the covariance structure of repeated outcome measures from the same subject and the same number of subjects in each group with/without a potential factor of interest. The study is certain to detect moderate ($B \geq 0.4$) differences in the analysis.

Table 6-1. Power calculation for linear mixed effects model based on the most common types of porphyria (AIP and PCT)

Sample size	ρ	B for time x factor of interest	Power
150	0.5	0.3	0.45
		0.4	0.72
		0.6	>0.99
	0.7	0.3	0.67
		0.4	0.91
		0.6	>0.99

7. Data Management

All study data will be collected via systems created in collaboration with the RDCRN Data Management and Coordinating Center and will comply with all applicable guidelines regarding patient confidentiality and data integrity.

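### Section 6.A names no patient random slope. Fitted with random intercepts, the time-by-factor test is anti-conservative if patients progress at different rates.

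*Combined protocol and SAP*

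**What the plan says.** Section 6.A (Clinical and Laboratory Analyses) plans "linear mixed effects models that account for the main effect of interest and its change over time". These models are also to handle "correlated data associated with repeat measurements on the same persons" and to include "random effects of clinical center and patient, as well as the effects of confounding variables". The text does not say whether the patient effect is an intercept, a slope or both. It fixes no residual covariance, degrees-of-freedom method or robust standard error.

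Section 6.B makes the target parameter clear: "the main interest is in determining whether the regression coefficient of the interaction between time and covariate of interest is zero or not". For power it says "we assume compound symmetry for the covariance structure of repeated outcome measures from the same subject", and the synopsis power statement likewise uses "a variance of outcome equal to 1 and a compound symmetric covariance structure". The headline result is 91% power for an interaction of 0.4 with 150 patients and correlation 0.7. Section 6.B then describes detection of moderate differences as a certainty.

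Two other places bear on the point. Research question A in Section 2 is "To characterize the natural history and clinical variability (e.g., age of onset, severity, progression) in EPP and XLP participants". Section 4.E.1 says "New data as described below will be collected every 1-2 years", and Section 4.E.3 allows two-year intervals for participants whose symptoms are stable.

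**The concern.** A random intercept per patient, with independent residuals, is the same thing as compound symmetry. It lets patients differ in level but not in rate of change. If rates do differ, each patient's true slope adds variance to the estimated group difference in slopes. An intercept-only model puts only part of that variance into its residual, so the reported standard error is too small and the test rejects too often.

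The exposed tests are those asking whether genotype, subtype or a biomarker alters the course of disease. Research question A treats variability in progression as something to be described, so zero slope variance is a doubtful default for this study. The power figure rests on the same assumption.

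**Working it through.** **Inputs from the plan (synopsis, 6.B):** 150 patients in two equal groups of 75; at least 3 follow-ups, so baseline plus 3 gives K = 4 visits; outcome variance 1; ρ = 0.7, so within-patient residual variance 1 − ρ = 0.3; β = 0.4; two-sided α = 0.05.

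**Assumed, not in the plan:** yearly visits; between-patient slope SD τ = 0.1 or 0.2 outcome-SD per year; outcome variance 1 at baseline; β taken as the group difference accumulated over the whole follow-up, because the plan does not define its time scale.

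**1. The plan's own figure.** A repeated-measures interaction F test with 3 measurements, and the difference of 0.4 appearing at one of them, has f² = 0.00889. Then λ = 150 × 0.00889 × 3 / 0.3 = 13.33 on 2 and 296 df, and power is 0.912 (stated 0.91). A linear-slope version with four visits gives nearly the same. The sum of squares of time is S = 5, so a patient's slope has variance 0.3/5 = 0.06. The SE of the group difference is √(2 × 0.06/75) = 0.040, the difference per year is 0.4/3 = 0.133, and 0.133/0.040 = 3.33, giving power 0.915. The 91% is sound under compound symmetry.

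**2. Type I error of the intercept-only fit.** For a balanced design:

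- true variance of a patient's slope: V = (1 − ρ)/S + τ²
- variance the random-intercept model uses: M = [(1 − ρ) + τ²S/(K − 1)]/S
- type I error: 2 × [1 − Φ(1.96 × √(M/V))]

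| K (yearly) | S | τ | V | M | SE ratio √(M/V) | Type I error |
|---|---|---|---|---|---|---|
| 4 | 5 | 0 | 0.0600 | 0.0600 | 1.00 | 0.050 |
| 4 | 5 | 0.1 | 0.0700 | 0.0633 | 0.951 | 0.062 |
| 4 | 5 | 0.2 | 0.1000 | 0.0733 | 0.856 | 0.093 |
| 6 | 17.5 | 0.1 | 0.0271 | 0.0191 | 0.840 | 0.100 |
| 6 | 17.5 | 0.2 | 0.0571 | 0.0251 | 0.663 | 0.194 |

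Simulation (6,000 runs per setting) agrees: 0.060 and 0.095 at four visits, 0.100 and 0.191 at six. Adding a random slope in the same simulations brings these to 0.048, 0.054, 0.050 and 0.051. At ρ = 0.5, which Table 6-1 also covers, four visits give 0.057 and 0.078.

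**3. Power of a correctly sized test.** 91% power corresponds to a standardized difference of 1.96 + 1.34 = 3.30. Slope variation divides this by √(V/0.06):

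- τ = 0.1: 3.30/√(0.07/0.06) = 3.06, power 86%
- τ = 0.2: 3.30/√(0.10/0.06) = 2.56, power 72%

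Starting from the 0.915 of the four-visit slope version gives 87% and 73%.

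**4. Mixed visit spacing.** Simulated random-intercept fits with ρ = 0.7, four visits, half the patients on two-year spacing and slope SD 0.2 in the annual group gave type I error of about 0.19 if the two-year group has the same slope SD. It was about 0.10 if theirs is half as large and 0.05 if it is zero. All patients on annual visits gave 0.09.

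**The case against.** The strongest reply is that the plan does not commit to an intercept-only model. Section 6.A names a center effect as well as a patient effect, lists within-patient correlation separately, and leaves the structure open. A patient random effect can include a slope. Compound symmetry is stated only as a planning assumption. A reader might infer that the plan specifies a compound-symmetry analysis and will therefore declare false progression differences. The documents do not support that: it depends on how the model is fitted and on whether slopes vary.

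The size is also assumed. Section 4.H.2 treats the stability of porphyrin levels over time as an open question. A slope SD of 0.2 per year would raise the outcome variance from 1 to 1 + 0.04 × 9 = 1.36 by year 3, a clear departure from the plan's constant variance. At SD 0.1 and four visits the excess is about one percentage point, and six visits is more than the planned minimum.

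It is also tempting to argue that one-to-two-year spacing makes matters worse because patients with long intervals carry more leverage. Two-year intervals are for participants with stable symptoms, who may well have less slope variation, and step 4 shows that the effect could then vanish or reverse.

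All of this stands and limits the claim. It does not remove it: nothing in the plan protects the interaction test, and an analyst following 6.A and 6.B together would most naturally fit random intercepts.

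**Conclusion.** The point holds as a gap in specification with a predictable direction of error. On the ordinary random-intercept reading, and if patients progress at different rates, the time-by-factor test is anti-conservative. Type I error is about 6% to 9% at four yearly visits and 10% to 19% at six, for slope SDs of 0.1 to 0.2 outcome-SD per year at correlation 0.7. Power of 91% becomes about 86% to 72%. With no slope variation there is neither inflation nor loss of power. Any further effect of mixed visit spacing is not established.

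The certainty claimed in 6.B for an interaction of 0.4 is not supported: Table 6-1 itself gives 0.72 at correlation 0.5, before any slope variation. The primary outcome in 6.A, the one-sample HADS comparison, does not use this model. The change is worth making because it is cheap and concerns the coefficient that 6.B singles out.

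**What to change.** In 6.A, specify a clinical-center random intercept plus a patient random intercept and random slope on time (unstructured 2 × 2 covariance), with Kenward-Roger or Satterthwaite degrees of freedom. If the slope variance cannot be estimated, keep the random intercept and use patient-level robust standard errors.

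In 6.B, add power under slope SDs of 0.1 and 0.2 beside the compound-symmetry figures, define the time scale of β, and replace the claim of certain detection with the computed power.

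This is a wording change only, with no new data, visits or patients. The downside is slightly wider intervals and less favourable power figures; if slopes do not vary, little is lost.
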